## Specimen Banking:

All collected samples are de-identified and will only contain the subject's study ID number and date/time of collection. Samples will be used by our team and could be shared with other investigators with appropriate ethics approval for investigation.

Biological samples (blood, urine, skin, and stool) will be processed, stored, and destroyed in accordance with protocols in place for biological samples. Biological samples for participants enrolled through the University of Alberta will be stored in the Canadian Biosample Repository at the University of Alberta; biological samples for participants enrolled in Quebec will be stored at the CHU Sainte Justine in the Institutional biobank under the name "Biobanque sur les troubles neuro-développementaux et les conditions associées".

#### Blood:

Blood will be drawn at three points throughout the study with a total minimum blood draw volume of 30.5 mL at each draw. Serum samples will be frozen immediately and stored at the respective biobanks.

Samples may be used in the future for purposes related to this research. On a separate consent form, the participant/caregiver may indicate permission to allow for samples to be kept and stored indefinitely after the end of the study for use in future research. Alternatively, samples may be destroyed upon completion of the study.

The samples are stored in the respective biobank facilities described above. A part of the sample will be used for analysis locally or shipped for analysis to other scientists approved by the study investigators. Samples collected for safety analyses will not be used for any other purpose. Safety labs drawn at each visit will have a minimum volume of 6mL and will be processed through the Alberta Health Services Clinical Trial Lab. Safety labs from the Universite de Montreal will be assessed locally as well. Banked samples will be stored and will be used in biomarker studies.

#### Urine:

Urine samples for safety labs, biomarker analysis, and cell culture will be collected at three points throughout the main study (and at extension visits). Urine derived cell lines will be obtained locally at Ste-Justine and/or at the Universite Laval. We will only collect urine for cell culture/biomarker studies until we have a viable sample and then urine will only be collected for

A Double-Blind, Placebo-Controlled Trial of Metformin in Individuals with Fragile X Syndrome

safety labs. Samples will be stored in one of the biobank facilities described above. Banked samples will be stored and used in biomarker studies.

#### Skin:

Skin sample will be collected at the baseline visit only if the participant/caregiver chooses to participate in this optional part of the study (separate consent form). As described above with regards to blood specimens, the participant/caregiver may indicate permission to allow for their skin sample to be kept and stored indefinitely at the biobank facility for use in future research; otherwise, samples will be destroyed upon completion of the study.

### Stool:

Stool samples will be collected at visits 1 and 3 of the main study (and at extension visits) and once from control participants at any point to be stored in the biobank facility for use in biomarker/other gut microbiome research if there is consent from the participant/caregiver to do so.

## 10) Provisions to Monitor the Data to Ensure the Safety of Subjects

It is the responsibility of the investigators to oversee the safety of the study for subjects seen at each site. This safety monitoring will include careful assessment and appropriate reporting of physical exam and lab abnormalities, adverse events, and SAEs as noted above. Adverse events, SAEs, and laboratory results will be reviewed by the DSMB after each SAE. The WCHRI DCC can do the ongoing data monitoring for both sites and prepare reports for the DSMB. Unanticipated problems posing risks to subjects or others and serious, unexpected adverse events associated with the research will be brought to the attention of the DSMB as soon as possible, accompanied by the evaluation of the event conducted by the site investigator.

The role of the DSMB will be to evaluate the participant risk versus benefit, consider factors external to the study when relevant information becomes available, such as scientific or therapeutic developments that may have an impact on the safety of the participants or the ethics of the trial, and make recommendations concerning continuation, termination, or other modifications of the trial based on the observed beneficial or adverse effects of the treatment under study, particularly in regards to a maximum tolerated dose in this study population. The PI will abide by the recommendation of the DSMB regarding stopping the study.

# 11) Withdrawal of Subjects

All subjects and their caregiver will be advised that they are free to withdraw from participation in this study at any time, for any reason, and without prejudice. Every reasonable attempt should be made by the investigator to keep subjects in the study; however, subjects must be withdrawn from the study if they/their caregivers withdraw consent to participate. The Page 35 of 47

1 November 2022 Pro00081059 investigator and/or the Research Coordinator must attempt to contact subjects who fail to attend scheduled visits by telephone or other means to exclude the possibility of an AE being the cause of withdrawal. Should this be the cause, the AE must be documented, reported, and followed as described in Section 10.

The site investigator also has the right to withdraw subjects from the study at any time for lack of therapeutic effect that is intolerable or otherwise unacceptable to the subject, for intolerable or unacceptable AEs, inter-current illness, noncompliance with study procedures, administrative reasons, or in the investigator's opinion, to protect the subject's best interest. If a subject is withdrawn before completing the study, the reason for withdrawal and the date of discontinuation will be recorded on the appropriate case report form (CRF). Whenever possible and reasonable, the evaluations that were to be conducted at the completion of the study should be performed at the time of premature discontinuation. Information gathered about a subject who has terminated the study early will be kept for analysis unless the subject/subject's caregivers specifically ask for this information to be removed from the analysis. Any unused biological samples will be destroyed.

Participants/caregivers will be informed of this as a part of the consent process and also reminded of this in the event of an early termination.

In addition, the study staff will explain to the participant/caregiver that, although it happens rarely, the sponsor may stop the trial early. This could be due to a number of reasons and would involve discontinuation of the participant's and caregiver's involvement in the study.

#### 12) Risks to Subjects

The most common anticipated risks due to participation in the study include anxiety, frustration, fatigue, or embarrassment during the answering of questionnaires, study assessments and testing, as well as during the medical history and exam. Breaks will be offered to subjects as needed.

Risks associated with blood draws include bruising, soreness, and slight risk of infection at the needle entry site for the blood draw. This site will be carefully cleaned prior to the draw and an appropriate dressing will be applied to the area. Risks associated with skin biopsies include bleeding, bruising, scarring, and slight risk of infection at the biopsy site. This site will be carefully cleaned prior to the biopsy and lidocaine or EMLA cream will be applied to numb the area.

Metformin is a Health Canada and FDA-approved medication with an established adverse events profile explained in the package insert. The clinical data suggest that metformin is safe and well-tolerated in diverse populations. The more common observed side effects during treatment with metformin are: diarrhea, nausea/vomiting, flatulence, asthenia, and abdominal or stomach

discomfort. The less common observed side effects during treatment with metformin are: headache, blurred vision, chest discomfort, cold sweats, coma, confusion, difficult or labored breathing, dizziness, feeling of warmth, or a heartbeat or pulse that is fast, irregular, pounding, or racing. Adverse events and toleration are similar between the liquid and tablet formulations of metformin. Safety labs will help rule out candidate at risk of serious side effects such as lactic acidosis and anemia. Patients and parents will be instructed about the symptoms of hypoglycemia and advised to consult urgently in case of such symptoms.

#### Adverse events

Serious Adverse Reactions associated with metformin include:

Lactic acidosis (rare in absence of renal insufficiency)

Anemia, megaloblastic

Hepatotoxicity

Hypoglycemia (rare in absence of concomitant use of sulfonylurea)

Common Reactions include:

Diarrhea

Nausea/vomiting

Flatulence

Asthenia (fatigue)

Indigestion

Abdominal discomfort

Anorexia

Headache

Metallic taste

Rash

Ovulation induction

Seeing symptoms of lactic acidosis (eg, weakness, fatigue, drowsiness, unusual muscle soreness, difficulty breathing, stomach pain with nausea, vomiting or diarrhea, feeling cold, dizziness, lightheadedness, slow or irregular heartbeat), requires discontinuation of metformin and immediate medical care. In case of suspicion of lactic acidosis, participants will be instructed to proceed to their local emergency room and contact the study doctor. Similarly, for signs of hypoglycemia such as shakiness, dizziness, sweating, and hunger, participants will be instructed to proceed to their local emergency room and contact the study doctor.

To monitor for any adverse events between visits, weekly phone calls during the first month will be made by study personnel to evaluate the presence of side effects. One additional phone call

A Double-Blind, Placebo-Controlled Trial of Metformin in Individuals with Fragile X Syndrome

will be made at Week 12 (Month 3), midway between visits 2 and 3. Phone calls will be made during the optional extension at weeks 1, 2, 3, 4, 20, 36, 52, 68, 84, and 100.

In case of serious adverse event, the blind will be removed by contacting the study doctor who will then open the envelope containing the subject identifier treatment status (placebo or metformin). Individualized sealed envelope will be given to the site study doctor from the Alberta Health Services Pharmacy Research Office (University of Alberta) and SPSR (CHU Sainte-Justine, University of Montreal). The Pharmacy Research Office and the SPSR will retain a copy of the randomization codes. The randomization of participants will be done directly in the REDCap shared database of the trial.

During the course of a clinical trial, Health Canada and the REB shall be informed of any serious unexpected adverse drug reaction:

- a. if it is neither fatal nor life threatening, within 15 days after becoming aware of the information; and
- b. if it is fatal or life threatening, within seven days after becoming aware of the information.

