## Data Safety and Monitoring Board (DSMB):

A DSMB for the Canadian centers located at the University of Alberta will collaborate and exchange information with the DSMB of the US site at the MIND Institute. The Canadian DSMB will include a minimum of two physicians who are independent of this study but who have significant expertise in carrying out psychopharmacological interventions in individuals with FXS. In addition, an independent statistician not involved with the study will be a member of each DSMB. The DSMBs will examine unblinded adverse events and clinical data on a semi-annual basis to review study progress and to advise whether the trial can be safely continued. The investigators and study staff will remain blinded throughout the trial. Any serious adverse events (SAEs) will be reported to the REB of each site and Health Canada in accordance with their respective reporting guidelines.

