### 15) Sharing of Results with Subjects

At the conclusion of the study, the possible medical benefit from the study will be reviewed with the subject and his or her caregiver. Participants/caregivers will not be unblinded at any point during enrollment. This is to prevent unconscious biases that may present as the trial progresses and to ensure quality data. Participants/caregivers will be unblinded once all study procedures and all statistical analyses for all subjects have been completed. Unblinding will be conducted by a study physician. If a subject/caregiver has to be unblinded for emergency purposes, then the subject/caregiver will be notified by the PI or site investigator.

The results of the study will also be published in a peer reviewed scientific journal that will be made publicly available through PubMed Central. In addition, after publication the results will be posted on the MIND Institute website under clinical trials.

Preliminary data may be presented annually at scientific meetings. Preliminary data may also be shared with the network of 22 USA National Fragile X Foundation (NFXF), Fragile X Clinical and Research Consortium clinics, and with the 20 countries involved with the NFXF International Consortium. Permission from Drs. [name] and [name] will be required prior to the presentation of Canadian derived data.

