### Randomization:

Allocation tables generated by the Data Coordinating Centre statistician have been uploaded to REDCap and sent to the Alberta Health Services Pharmacy Research Office (University of Alberta) and SPSR (CHU Sainte-Justine, University of Montreal). Once the study coordinator has randomized a participant in REDCap (done separately for each site), the randomization number that is generated will be sent to the respective pharmacy, which will then prepare the drug or placebo based on the number they are given and the table that has been provided to them by the DCC.

Participants will be randomized to treatment or control arm with a 1:1 allocation ratio, stratified by sex and using permuted blocks of randomly varied sizes 2 and 4. Participant randomization will be performed in REDCap, based on allocation tables that have been generated and uploaded by the Data Coordinating Centre statistician. REDCap maintains an automated audit trail which includes the assigned study identification number, treatment allocation, and date and time of the transaction.

The randomization process will be performed the same way at both sites, i.e. randomization to treatment or control arm with a 1:1 allocation ratio stratified by sex and using permuted blocks of randomly varied sizes 2 and 4.

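### The protocol has the site study doctor open the treatment code for any serious adverse event, which contradicts its statement that investigators and study staff stay blinded

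*Combined protocol and SAP*

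**What the plan says.** Three places govern who learns a treatment assignment during the blinded phase.

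- **Section 12, Adverse events.** "In case of serious adverse event, the blind will be removed by contacting the study doctor who will then open the envelope". The envelopes are per participant and held at the site: "Individualized sealed envelope will be given to the site study doctor from the Alberta Health Services Pharmacy Research Office" (and, for Montreal, from the hospital's research pharmacy service). The same paragraph says both pharmacies keep a copy of the codes.
- **Section 8, Data Safety and Monitoring Board.** "The DSMBs will examine unblinded adverse events and clinical data on a semi-annual basis". In the same paragraph: "The investigators and study staff will remain blinded throughout the trial". No exception is attached.
- **Section 15, Sharing of Results with Subjects.** "Participants/caregivers will not be unblinded at any point during enrollment", with this provision: "If a subject/caregiver has to be unblinded for emergency purposes, then the subject/caregiver will be notified by the PI or site investigator".

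Other sections describe the roles involved. Section 18 gives the study doctor discretion over dose modification during titration. Section 10 has the site investigator evaluate serious, unexpected events for the DSMB. Section 7 assigns the CGI ratings to a clinician who is not further identified. Section 18 (Randomization) describes allocation "stratified by sex and using permuted blocks of randomly varied sizes 2 and 4", carried out separately at each site.

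**The concern.** Read as written, Section 12 makes code-breaking automatic. An SAE that is plainly unrelated to study drug, or already resolved when reported, would still lead the site study doctor to open the envelope. That doctor is among the investigators and staff whom Section 8 says stay blinded, so a site cannot follow both sentences.

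What is at stake is judgement exercised after the arm is known:

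- **Dosing.** The study doctor decides on dose modification for that participant.
- **Safety evaluation.** If the study doctor is also the site investigator, the event may be evaluated for the DSMB with the arm known. Safety and tolerability is the first objective in Section 2.
- **CGI-I.** This is a clinician rating at weeks 8 and 16. If the study doctor is the rater, ratings after the code break are unblinded.

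The protocol does not say whether a person who has opened an envelope may go on assessing or managing that participant.

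**Working it through.** The contradiction is textual and does not depend on alpha, power or sample size. The plan states no figure on this point to reproduce.

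**1. The rules side by side**

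| Section | Who learns the arm | Trigger |
|---|---|---|
| 12, Adverse events | Site study doctor | Any SAE, no further condition |
| 8, DSMB | DSMBs only; site personnel stay blinded | Semi-annual review |
| 15, Sharing of Results | Subject/caregiver | Emergency only |

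Sections 12 and 8 conflict directly for the study doctor. Sections 12 and 15 concern different people and can both be followed, but the Section 12 trigger is wider, since not every SAE is an emergency.

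**2. Is the doctor's knowledge needed for reporting?** Section 8 already gives the DSMBs unblinded adverse-event data. Section 10 says the Data Coordinating Centre (DCC) can prepare DSMB reports. Section 12 says the pharmacies retain the codes, and Section 18 says the DCC statistician generated the allocation tables. A route that bypasses the site study doctor therefore already exists.

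**3. Scale**

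Inputs: 120 participants (60 per group, Section 8 power paragraph). The documents give no SAE rate, so I assume a proportion p of 1% to 5% of participants with an SAE.

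Expected code breaks = 120 × p. Probability of at least one = 1 − (1 − p)^120.

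| Assumed p | Expected code breaks | P(at least one) |
|---|---|---|
| 1% | 120 × 0.01 = 1.2 | 1 − 0.99^120 = 0.70 |
| 2% | 120 × 0.02 = 2.4 | 1 − 0.98^120 = 0.91 |
| 5% | 120 × 0.05 = 6.0 | 1 − 0.95^120 = 0.998 |

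The rule would probably be used, but for few participants.

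**4. Spill-over to the next participant (secondary)**

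Inputs: block sizes 2 and 4 (Section 18). The protocol does not give their frequencies; I assume they are equally likely. A participant is then equally likely to hold any of 2 + 4 = 6 block positions. The probability that the next participant in the same sex-by-site list has the opposite arm is:

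- block of 2: first position 1; second position 0.5 (a new block starts);
- block of 4: first, second and third positions 2/3 each; fourth position 0.5.

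Average = (1 + 0.5 + 2/3 + 2/3 + 2/3 + 0.5) / 6 = 4/6 = 0.67, against 0.50 with no information.

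**The case against.** **The sentence may be meant for emergencies.** Earlier in the same subsection, participants with suspected lactic acidosis or hypoglycaemia are sent to the emergency room and told to contact the study doctor. Section 8 could also be the general rule, with Section 12 a specific exception. This may be what the authors intended, but it does not narrow the text. A paragraph on telephone calls separates the emergency-room instructions from the SAE sentence, which carries no condition of its own. Section 8 signals no exception.

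**The reach is limited.** This stands in large part, and it rules out several stronger readings that a reader might infer:

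- *That the study doctor is an outcome rater.* Section 7 names only a clinician for the CGI. The overlap is possible but not stated.
- *That the primary outcome is compromised.* Expressive language sampling is done by an examiner following a script, then transcribed and analysed by computer. The study doctor has no stated role in it.
- *That caregiver-rated scales are unblinded.* Section 12 does not say the caregiver is told, and Section 15 says caregivers are not, emergencies aside.
- *That Sections 8, 12 and 15 are all mutually incompatible.* Only Sections 8 and 12 collide.
- *That the next participant's arm becomes certain in a block of 2.* That requires knowing the block size and the position revealed, which randomly varied sizes conceal. The 0.67 is a long-run average. It is useful only to someone who tracks enrolment order within sex at that site, and nothing suggests that allocation is steered.

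**Dose discretion is mainly early.** Section 18 gives the broad discretion in the first four weeks; later adjustments are tied to illnesses with gastrointestinal symptoms. This shortens the exposure but does not remove it.

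**Conclusion.** The point holds in a limited form. Section 12 requires the site study doctor to break the code for any SAE. This contradicts Section 8 and is wider than the emergency exception in Section 15. It unblinds a person with dosing discretion, who may also be the evaluator of the event and the CGI-I rater.

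On an assumed SAE rate of 1% to 5% of 120 participants, about 1 to 6 people would be affected. Each envelope covers one participant. The spill-over of 0.67 against 0.50 assumes equally likely block sizes and is secondary. The documents do not support a claim of bias in the primary analysis or in the caregiver-rated scales. The case for change is that the contradiction is plain, the unblinding is unnecessary for reporting, and the correction is cheap.

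**What to change.** Amend Sections 8, 12 and 15 so that they agree:

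1. State that an SAE does not by itself lead the site study doctor to open the envelope.
2. Keep the emergency code-break route that Section 15 already foresees, and refer to it in Sections 8 and 12 as the stated exception.
3. Where the DSMB or a regulator needs the assignment for reporting, have the research pharmacy or the DCC supply it directly, not through the site study doctor.
4. Log each code break: date, reason, and who learned the assignment.
5. Identify the CGI-I rater, and state whether a person who has learned an assignment may go on rating that participant.

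Intention-to-treat analysis is already specified in Section 8 and needs no change. The cost is a wording amendment and a short note to the two pharmacies. No new staff are needed, because the code holders are already in place. The downside is one extra step for non-urgent SAEs.

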#### Other unanticipated risks:

Drug-related risk: Prediction of drug effects or side-effects in any individual cannot be done with certainty, and unexpected potentially harmful effects could possibly occur. The close clinical and laboratory monitoring of subjects is intended to detect any such unanticipated side-effects so that appropriate corrective measures can be implemented in a timely manner.

Genetic testing risk: Since genetic analysis will be performed to identify the basis of clinical variation and differential response to metformin in both a targeted and unbiased manner, it may be possible to discover some "incidental findings" i.e. information that we were not looking for. This information related to the participant's health could have a direct impact on their clinical care in some cases. We will follow the guidelines from the American College of Medical Genetics reported previously and widely adopted including in Canada (Genet Med. 2013 Jul; 15(7): 565–574).

In the event that a potential significant and actionable result is found and that preventive measures or treatments are available for the participants, they will be notified through the study doctor. In this situation, the study doctor will recommend to repeat these tests to confirm the research results. A meeting with a geneticist and/or a genetic counsellor will be organized to discuss the pros and cons of further testing in the clinical set up If the clinical testing confirms the research results, the medical geneticist will proceed as he/she would do normally in the clinical setting and the health information will be recorded in the participant's medical chart.

Genetic test results for children will be communicated to the family if there is actionable

conduct. As suggested by the American College of Medical Genetics, results for which an adult onset or for which there is no interventions will not be disclosed as this is a research study. In addition, results related to non-paternity will not be disclosed in the context of this research testing for genes affecting the clinical presentation and drug response.

Possible ineffectiveness of treatment: Some patients may not benefit from the treatment provided. If their condition deteriorates to the point that requires immediate effective treatment, they will be discontinued from the study and referred for such treatment.

